### **Secondary outcomes**

We will use the approaches described in analyses 1-3 above to evaluate the impact of the intervention on the secondary outcome measures listed in the pre-registration:

1. Flu vaccination within 7 days [ Time Frame: Within 7 days of when patient is randomized ]

Received flu vaccination

2. Flu diagnosis [ Time Frame: During the 2021-22 flu season (Up to 8 months, from the time the patient is randomized through April 30, 2022) ]

Received a "high confidence flu" diagnosis (with positive polymerase chain reaction [PCR]/antigen/molecular test) and/or "likely flu" diagnosis (as assessed via International Classification of Disease [ICD] codes or Tamiflu administration or positive PCR/antigen/molecular test)

Note that "likely flu" is a superset of the "high confidence flu" diagnoses.

3. Flu complications [ Time Frame: During the 2021-22 flu season (Up to 11 months, from the time the patient is randomized through July 31, 2022) ]

Diagnosed with flu-related complications

4. Flu vaccination (among subject cohabitants) within 28 days [ Time Frame: Within 28 days of when the study subject is randomized ]

Cohabitant of study subject received flu vaccination

This analysis will exclude patients who are both cohabitants of a subject and subject themselves

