With the current study, we hypothesize that, among incentives of equal perceived EV or equal implementation costs, people are more likely to get vaccinated in response to lotteries with very high payoffs than to small certain cash payout or slightly higher-probability, more moderate payoffs. In particular, given the potential appeal of official state lottery tickets, we will include the promise of Pennsylvania scratch-off lottery tickets among our study arms. We further

hypothesize that lotteries will outperform simple reminders (encouraging respondents to get the flu shot at their upcoming appointment) and the standard of care, representing the ambient healthcare system and public health campaigns to increase vaccination.

Our specific aims are:

- 1. Evaluate whether providing any monetary incentive has a larger effect on vaccination rates than simple reminders or no message.
- 2. Evaluate whether lotteries are more effective than an equivalent-cost, certain \$1 cash payout.
- 3. Subject to available sample, evaluate which variations in prize-probability combinations and their presentation are most effective, allowing us to model the curvature of the prize-probability frontier.

PROCEDURES

Research Design

Patients at Geisinger who have a primary or specialty care appointment scheduled during the study period will be randomly assigned to a study arm. Outcomes during the 2021-2022 flu season will be compared between study arms.

Study Population

There are 2 separate populations to consider in the current study: the primary target population that will be randomized into an experimental condition and potentially contacted, and the household members of the primary population, who will not experience an intervention and will only be included for data analysis purposes.

1) Primary target population

Inclusion Criteria:

- Aged 18 or older
- Geisinger primary care provider (PCP) assigned
- Upcoming appointment with PCP or select specialist who stocks and can administer the vaccine during the study period

Exclusion Criteria:

- Has contraindications for flu vaccination
- Note: we will respect opt-out communication preferences, but will include patients in the study if they haven't opted out of at least one communication modality employed

2) Secondary population (data analysis only): Household members

Inclusion Criteria:

- Household members of primary target population
- Current Geisinger patient

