### Power analysis

The study team planned to enroll at least 9,806 patients per study arm. Assuming a baseline vaccination rate of 50%, this sample would allow 80% power to detect a 2% absolute percentage-point difference, or a 4% relative difference, between any two groups.

In August, 2021, we completed an analysis of the anticipated number of eligible patients in the study. This analysis suggested that our sample would be large enough to run four study arms (i.e., we projected that we would enroll more than 39,224 participants, but fewer than 49,030, the number that would have been required to add a fifth arm). Therefore, we proceeded with running only the priority four pre-registered study arms, and we anticipate enrolling a total of at least 39,224 patients across those four groups.

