### Sample and Randomization

The sample includes patients who have an upcoming primary or specialty appointment where they can get a flu shot, and who, according to Geisinger's records, have not yet received a flu shot in the 2021–22 flu season. Patients are also age 18 or older, are not contraindicated for flu shots, and have an assigned Geisinger PCP. All patients are also eligible to receive text messages from Geisinger.

The four study groups include:

1. Pennsylvania (PA) Lottery Scratch-Off Financial Incentive - Participants in this arm receive a message stating that they will receive a PA lottery \$1 scratch-off ticket if they get a flu shot at an upcoming appointment. The message will mention that they could win \$5,000 (the top prize for the scratch-off game).
2. Certain Cash Payout Financial Incentive - Participants in this arm receive a message stating that they will receive \$1 in cash if they get a flu shot at an upcoming appointment.
3. Reminder / Active Control (No Financial Incentive) - Participants in this arm receive a message stating that they can get a flu shot at an upcoming appointment. These participants will not be offered a financial incentive for getting a flu shot.
4. No Intervention: No Treatment Control - No additional contact beyond standard Geisinger flu shot communications

Each day, the study team receives a list of eligible patients with flu-shot-eligible appointments in the upcoming 3 days. Patients with appointments in 3 days are randomized into the 4 groups described above. Those in groups 1-3 receive their first messages 3 days prior to their appointment.

All patients who are sent 3-day messages are sent 1-day messages, as long as they appear on the list of eligible patients the day prior to their appointment. There are two reasons patients may not appear in that list: 1) their appointment is rescheduled and they no longer have a flu-shot-eligible appointment scheduled on that date, or 2) Geisinger records are updated indicating the patient got a flu shot after randomization but before the 1-day reminder list is created, rendering the patient ineligible for a flu shot at their appointment.

In cases where a patient cancels their appointment or reschedules it for a different day, they are not sent a 1-day message.

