### **Planned Analyses**

#### ***Primary Outcome***

Flu vaccination at appointment [ Time Frame: 3 days after patient is randomized ]

**Question 1:** Can lottery incentives increase flu vaccination rates better than equivalent-value cash payouts, active control messages, or no messages?

*Analysis 1a (Confirmatory):* We will test the hypothesis that patients who are sent messages with promise of an official state lottery ticket if they get vaccinated (patients randomized to message group 1) will exhibit improved flu vaccination rates compared with patients who are sent messages offering a certain \$1 cash payout if they get vaccinated (group 2).

*Analysis 1b (Confirmatory):* We will test the hypothesis that patients who are sent messages with promise of an official state lottery ticket if they get vaccinated (patients randomized to message group 1) will exhibit improved flu vaccination rates compared with patients who are sent active control messages (group 3).

*Analysis 1c (Confirmatory):* We will test the hypothesis that patients who are sent messages with promise of an official state lottery ticket if they get vaccinated (patients randomized to message group 1) will exhibit improved flu vaccination rates compared with patients who are sent no messages (group 4).

For analyses 1a through 1c, we will run an OLS regression, with a dummy variable coding for no message (group 4), active control message (group 3), cash (group 2), or state lottery (group 1).

**Question 2:** Do active control messages encouraging flu shots at an upcoming appointment increase flu vaccination rates?

*Analysis 2 (Confirmatory):* We hypothesize that patients who are sent active control messages encouraging them to get a flu shot without any associated incentives (group 3) will be more likely to get vaccinated than those in the no-contact control group (group 4). To assess this hypothesis, we will employ OLS regression with a categorical predictor variable coding for group (group 3 vs. group 4).

**Question 3:** Do small cash incentives increase flu vaccination more than active control messages or no messages?

*Analysis 3a (Exploratory):* We will test whether patients sent text messages promising small cash incentives in exchange for vaccination (group 2) are more likely to get vaccinated than those who are sent active control messages (group 3).

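### Secondary outcome 4 (cohabitant flu vaccination) has no stated unit of analysis, standard-error estimator or provision for clustering, although cohabitants take their arm from a linked subject

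*SAP*

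**What the plan says.** The SAP, under Secondary outcomes, covers all four measures with one sentence: "We will use the approaches described in analyses 1-3 above to evaluate the impact of the intervention on the secondary outcome measures". The approach it points to is in the Primary Outcome section, where for analyses 1a to 1c "we will run an OLS regression, with a dummy variable coding for no message (group 4"), and likewise for the other three groups. Analyses 2, 3a and 3b are also OLS on group. None of them names a standard-error estimator.

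Outcome 4 itself is defined as "Cohabitant of study subject received flu vaccination", timed from the randomization of the study subject. One special rule is attached: "This analysis will exclude patients who are both cohabitants of a subject and subject themselves". The SAP does not say whether a row is a cohabitant or a subject, how several cohabitants of one subject are combined, or which arm and start date apply to a cohabitant of two subjects.

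The Protocol, under Study Population, describes "household members of the primary population, who will not experience an intervention and will only be included for data analysis purposes". Its Recruitment and Enrollment paragraph expects 80,000 household members against at least 39,224 subjects, and says that only the subjects will be contacted.

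The SAP's one household provision, under Sensitivity analyses and robustness checks, repeats the analyses after removing patients who share an address with another patient in the study. The same section says that patients were randomized independently of household.

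**The concern.** Because only subjects are randomized and messaged, a cohabitant's arm has to come from a linked subject. All cohabitants of a single subject therefore share an arm, and an average near two per subject means that many subjects would contribute several rows. People at one address plausibly make similar vaccination decisions. Treating their rows as independent counts the same information more than once. Confidence intervals come out too narrow, and a nominal 5% test rejects too often.

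Outcome 4 is the SAP's only planned test of an effect on household members, so a false spillover finding would have no second analysis to check it. The unit, linkage rule and variance estimator are also all open, which would allow them to be chosen after results are seen. The Project status section says that no secondary outcome had been extracted or analyzed, so as of that text they could still be fixed in advance.

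**Working it through.** **The plan's own figure.** For 50% against 52%, 80% power and a two-sided 5% test (alpha and sidedness are inferred; the SAP does not state them):

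n = [1.960·√(2·0.51·0.49) + 0.842·√(0.50·0.50 + 0.52·0.48)]² / 0.02² = 9,806 per arm.

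This reproduces the SAP's figure, and 4 × 9,806 = 39,224. The calculation concerns subjects and is not in dispute. No sample-size figure is given for cohabitants.

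**Inputs for outcome 4**
- Cohabitants per subject: 80,000/39,224 = 2.04, from the Protocol. It precedes the removal of cohabitants who are subjects, so the analysed mean may be lower.
- Lower values, for range only: 1.63, which is 80,000/49,030, and 1.5. Both are assumptions. The SAP says "we projected that we would enroll more than 39,224 participants, but fewer than 49,030", but the Protocol pairs its 80,000 with 39,224.
- Intraclass correlation (ICC): not in the documents; assumed 0.1 to 0.5.
- Spread of household size: not in the documents; assumed between near-equal whole numbers and Poisson.

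**Formulas**, with k the number of cohabitants linked to a subject and one row per cohabitant:
- Design effect DE = 1 + (E[k²]/E[k] − 1)·ICC. For Poisson sizes, this is 1 + mean·ICC.
- True error of a nominal 5% test = 2·(1 − Φ(1.96/√DE)).
- Correct standard error divided by naive standard error = √DE.

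For Poisson sizes with mean 2.04 and ICC 0.5, DE = 1 + 2.04·0.5 = 2.02, √DE = 1.42, and the true error is 2·(1 − Φ(1.379)) = 16.8%.

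| Mean per subject | Sizes | DE, ICC 0.1 to 0.5 | True error | √DE |
|---|---|---|---|---|
| 2.04 | near-equal | 1.106 to 1.529 | 6.2% to 11.3% | 1.05 to 1.24 |
| 2.04 | Poisson | 1.204 to 2.020 | 7.4% to 16.8% | 1.10 to 1.42 |
| 1.63 | near-equal | 1.077 to 1.387 | 5.9% to 9.6% | 1.04 to 1.18 |
| 1.63 | Poisson | 1.163 to 1.816 | 6.9% to 14.6% | 1.08 to 1.35 |
| 1.5 | near-equal | 1.067 to 1.333 | 5.8% to 9.0% | 1.03 to 1.15 |
| 1.5 | Poisson | 1.150 to 1.750 | 6.8% to 13.8% | 1.07 to 1.32 |

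**Check by simulation** (this tests the formula and the remedy, not this trial). Two arms of 9,806 subjects, Poisson mean 2.04, beta-binomial outcomes at a 50% rate, 3,000 runs. For ICC 0.1, 0.3 and 0.5, naive errors rejected 7.0%, 12.1% and 17.3% of the time. Errors clustered on the subject rejected 4.9%, 4.4% and 5.3%. In separate runs, heteroskedasticity-robust errors matched plain OLS to 0.1 point, so they do not help.

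A four-arm version (ICC 0.3, 2,000 runs) put two subjects at 10% or 30% of addresses and linked cohabitants to the first-randomized subject. Naive OLS rejected 12.1% and 11.1%; errors clustered by address rejected 5.3% and 4.5%.

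**Do the existing checks cover it?** No. The shared-address sensitivity analysis, even if extended to outcome 4, leaves several non-subject cohabitants under one subject. The logistic, message-delivery and covariate-adjusted checks do not deal with dependence within households.

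**The case against.** The strongest reply is that this is silence, not error. The exclusion rule and the 80,000 records fit one yes/no per subject as well, since one must still say which cohabitants count and pull their records. Reusing analyses that compare randomized patients, and timing the outcome from the subject's randomization, lean that way. With one row per subject, the clustering of cohabitants under a subject disappears. OLS also does not rule out clustered errors.

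Much of this stands. The outcome's title, which speaks of vaccination among cohabitants, favours cohabitant rows, but the unit is not settled. A reader might infer that the SAP commits to standard errors that are too small. It names none, so what the text establishes is the missing provision.

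A reader might also take 6% to 17% as limits on the error. They are not: the top needs the highest ICC, the highest mean and Poisson sizes together, while ICC 0.05 with Poisson mean 1.5 gives 5.9%. Nor do the figures carry over to the other outcomes, which are measured on subjects.

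The reply does not remove the need for a rule. Under either unit the SAP lacks a sentence. Independent randomization within addresses can also leave a cohabitant linked to two arms and two 28-day periods, which is part of the same household-linkage gap.

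**Conclusion.** The point holds as a should-fix gap in one secondary outcome. Three things are certain from the text: outcome 4 is sent to OLS with arm dummies; neither unit, variance estimator nor clustering is given; and a cohabitant's arm can come only from a linked subject.

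The consequence rests on two conditions that the documents do not settle: one row per cohabitant, and positive correlation within households. If both hold, conventional and heteroskedasticity-robust errors are too small. Over the assumed scenarios, a nominal 5% test would reject about 6% to 17% of the time, and correct standard errors would be 3% to 42% larger. These sizes are illustrative. Confidence is medium because of those conditions.

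**What to change.** Add to the SAP text for outcome 4:
- **Unit.** State whether a row is a cohabitant or a subject; if a subject, say how several cohabitants are combined.
- **Variance.** Keep OLS and use standard errors clustered by address. This is also valid with one yes/no per subject, because subjects can share an address.
- **Linkage.** Set one rule in advance for the arm and 28-day start date of a cohabitant linked to more than one subject, for example the first-randomized subject with a fixed same-day tie rule. Under that example, the address carries the arm.
- **Stated limitation.** The SAP says "Each day, the study team receives a list of eligible patients with flu-shot-eligible appointments in the upcoming 3 days", and eligibility requires that patients "have not yet received a flu shot". Whether a housemate later becomes a subject can therefore depend on the first subject's arm. This affects both the SAP's existing exclusion of cohabitants who are subjects and any restriction to single-subject addresses. Clustering does not remove that selection, so say so.

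The cost is a few lines of text, a standard-error option, and an address identifier plus vaccination dates in the household extract. The interval for this outcome becomes 3% to 42% wider over the assumed range. At the SAP's 50% rate (none is given for cohabitants), corrected power for a 2-point difference is 80% to 97% with all 80,000 cohabitants (20,000 per arm; means 2.04 and 1.63). With 1.5 per subject and 39,224 subjects (14,709 per arm) it is 74% to 91%. The outcome stays usable.

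### The 28-day cohabitant vaccination outcome keeps people already vaccinated before the linked subject was randomized, which shrinks the estimated spillover effect; a date filter set before extraction is a cheap improvement

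*SAP*

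**What the plan says.** **Outcome.** SAP, Secondary outcomes, item 4: "Cohabitant of study subject received flu vaccination", with the time frame "Within 28 days of when the study subject is randomized". One exclusion follows: "This analysis will exclude patients who are both cohabitants of a subject and subject themselves".

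**Analysis.** The same section says: "We will use the approaches described in analyses 1-3 above to evaluate the impact of the intervention on the secondary outcome measures". Those analyses are OLS comparisons of the four arms, so the estimate is a risk difference. They include no term for vaccination earlier in the season.

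**Who the cohabitants are.** Protocol, Study Population, gives two criteria for the secondary population: "Household members of primary target population" and "Current Geisinger patient". There is none on current-season vaccination, age or contraindication. Neither document says how a cohabitant's earlier 2021-22 shot is coded.

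**Contrast with subjects.** SAP, Sample and Randomization, limits subjects to patients who "have not yet received a flu shot in the 2021–22 flu season" according to the health system's records, and it excludes those with contraindications.

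**Timing.** The Protocol starts the intervention at about 9/1/21. The SAP randomizes daily, three days before each appointment, and gives 12/31/2021 as primary completion. SAP, Project status, says that no secondary outcome data have been extracted or analyzed.

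**The concern.** A cohabitant vaccinated before the linked subject was randomized has a fixed outcome. If only shots in the 28 days count, that person is a certain non-event; if any shot by day 28 counts, a certain event. In both cases the message sent to the subject can make no difference, so the person adds nothing to the arm contrast except a larger denominator. Randomization is spread over the autumn, so the share of such people should rise for subjects randomized later.

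At stake is how the household spillover result is read. The estimate would mix the effect on people who could still be vaccinated with zeros from people who could not. It would depend on the calendar mix of enrolment. It would also not be comparable with the subjects' own 7-day vaccination outcome, which is measured only in people unvaccinated at entry.

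**Working it through.** **1. The plan's own figure.** The documents give no sample size for the cohabitant outcome. The stated 9,806 per arm for subjects (50% vs 52%, 80% power) reproduces exactly with a two-sided 0.05 test (alpha and sidedness assumed), pooled variance and no continuity correction. This point does not affect it.

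**2. Inputs.**
- Cohabitants: 80,000 expected (Protocol, Recruitment and Enrollment), so 80,000 / 4 = 20,000 per arm if spread evenly (assumption).
- q, share vaccinated before the linked subject's randomization: not given; 10-50% used for the effect size and 20-50% for precision.
- r, 28-day uptake among the rest: not given; 10-20% assumed.
- d, risk difference among those still unvaccinated: not given; 1 or 2 points assumed.
- Household clustering is ignored.

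**3. Effect size.** Earlier vaccination precedes randomization, so q is equal across arms in expectation.
- Earlier shots coded 0: (1-q)(r+d) - (1-q)r = (1-q)d.
- Earlier shots coded 1: [q+(1-q)(r+d)] - [q+(1-q)r] = (1-q)d.

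The attenuation is the same on either coding. For d = 2.0 points:

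| q | all cohabitants | unvaccinated only |
|---|---|---|
| 10% | 1.8 | 2.0 |
| 30% | 1.4 | 2.0 |
| 50% | 1.0 | 2.0 |

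**4. Precision.** Ratio of z, restricted over all-cohabitant, for the same underlying effect:
- Only in-window shots count: sqrt{[1-(1-q)r] / (1-r)}
- Earlier shots count as successes, with m = q+(1-q)r: sqrt{m(1-m) / [(1-q)r(1-r)]}

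| q | r | z gain, in-window only | z gain, earlier shots as successes |
|---|---|---|---|
| 20% | 10% | 1.1% | 67% |
| 20% | 20% | 2.5% | 34% |
| 40% | 15% | 3.5% | 81% |
| 50% | 10% | 2.7% | 135% |
| 50% | 20% | 6.1% | 73% |

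Worked example at q = 40%, r = 15%: sqrt(0.91 / 0.85) = 1.035. For the second coding m = 0.49, and sqrt(0.2499 / 0.0765) = 1.81.

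**5. Power.** 20,000 cohabitants per arm before restriction, r = 20%:

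| q | d | all, in-window only | all, earlier shots as successes | unvaccinated only |
|---|---|---|---|---|
| 30% | 1 point | 51.5% | 29.1% | 54.5% |
| 50% | 1 point | 37.8% | 17.4% | 41.7% |
| 50% | 2 points | 90.4% | 53.4% | 93.5% |

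When only in-window shots count, restriction gains about 3 to 4 points of power. The large differences appear only under the other coding.

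**The case against.** **The SAP never says that earlier vaccinees are scored.** True. It gives a short label, a window and one exclusion, and their inclusion follows from the absence of any baseline criterion. But an analyst following the text has no basis for removing them.

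**The window already means in-window shots.** This is the better reading, and the wording parallels the 7-day outcome for subjects. It stands, and with it the precision loss is small. A reader might infer from the 34-135% figures that the analysis is badly underpowered; the documents do not support the coding that produces them, although they do not expressly rule it out.

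**An all-cohabitant average is a legitimate estimand.** It is: extra vaccinations per cohabitant of a messaged patient. The SAP does not say that it was chosen, however, so keeping it as a sensitivity analysis loses nothing.

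**The dilution depends on the scale.** This stands. With in-window coding the risk ratio is unchanged, because (1-q) cancels. The log odds ratio shrinks about 2-12% for q of 20-50%, r of 10-20% and a 2-point effect (7% at q = 40%, r = 15%). The SAP plans logistic regression as a robustness check, but does not say explicitly that it extends to secondary outcomes. The main estimate remains a risk difference.

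**q may be low.** For subjects randomized in early September it probably is. Nothing in the documents fixes it.

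**Conclusion.** The point holds as a cheap improvement to a secondary outcome. As written, the denominator includes cohabitants whose result was settled before the linked subject was randomized. The OLS risk difference therefore understates the effect among those still able to be vaccinated by the factor (1-q): 10-50% too small for an illustrative q of 10-50%. On the natural reading of the window, z is about 1-6% lower than in the restricted analysis (q of 20-50%, r of 10-20%). Both q and r are assumptions.

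Two stronger conclusions are tempting and are not supported. The first is that the comparison is biased between arms or prone to false positives: earlier vaccination precedes randomization and is balanced in expectation, so the test is valid. The second is that a null spillover result could be put down to the denominator alone: with in-window counting, the power lost in the cases shown is about 3 to 4 points, which would seldom turn a detectable effect into a null. The primary analysis is untouched.

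**What to change.** Add to the SAP, before secondary data are extracted:

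- Restrict the outcome 4 analysis to cohabitants with no recorded 2021-22 flu shot dated before the linked subject's randomization date. Judge this by the date of vaccination, which the arm cannot affect.
- Count only shots dated from that day through day 28.
- State whose randomization date applies when a cohabitant is linked to more than one subject.
- Report the number excluded by arm.
- Keep the all-cohabitant result as a sensitivity analysis.

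An age floor of 6 months at the randomization date may be added, in line with the recommendation cited in the Protocol's background. Use a contraindication filter only if it rests on records dated before randomization; the Protocol's Data Sources section does not list contraindications among the household data.

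**Cost.** A few lines of text and a date filter on vaccination data that the Protocol already plans to obtain for household members. The analysis set gets smaller, but those removed carry no information on the effect. It is also a late refinement of a pre-registered secondary outcome population, made after the primary outcome was analyzed, so it should be disclosed as such.
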